Effects of Ivabradine on residual myocardial ischemia after PCI evaluated by stress echocardiography.

Protocol Version 2.1

Date 15/09/2015

NCT number: not available

Investigators: [name]*, [name]*, [name]*, [name]*, [name]*, [name]*, [name]*, [name] PhD* and [name]*.

*Cardiovascular, Respiratory, Geriatric, Anesthesiologic and Nephrologic Sciences Department, Umberto I Hospital, Sapienza University of Rome, Italy.

INTRODUCTION

Stable angina is a syndrome characterized by a transitory condition of acute myocardial ischemic attacks caused by an imbalance between myocardial perfusion and metabolic demand [1]. The antianginal drugs and the percutaneous coronary revascularization, are essential to treat the persistent symptoms. However, in some cases, when small vessels or side branches are significantly involved with hard or impossible reperfusion, drug therapy is the only strategy to prevent the worsening of ischemic heart disease and to reduce the symptoms. Heart rate is the major determinant of cardiac output and myocardial oxygen consumption, therefore the reduction of heart rate in patients with stable angina can be considered a goal of the therapy [2]. Ivabradine is an antianginal agent that specifically inhibits the pacemaker (If) current, resulting in selective HR reduction with no negative effects on blood pressure and inotropism [3]. In patients with chronic heart failure, Ivabradine improves clinical outcomes if used with beta-blockers under well documented efficacy and safety [4].

In previous studies, Ivabradine reduced anginal symptomatology but has not clearly demonstrated improvements of the outcomes in patients with chronic ischemic disease without left-ventricular systolic dysfunction [5-7]. More recently, in CONTROL-2 Study, in patients with stable angina, the combination of the two therapies ivabradine and β -blockers together demonstrated good tolerability, safety, and also pronounced clinical improvements, compared to β -blockers up titration [8]. Moreover, an interesting SHIFT substudy showed the reversed LV remodeling with marked reductions of LV volumes and significant improvements of LV ejection fraction (LVEF) in patients treated with Ivabradine [9].

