In this context, in order to define the role of Ivabradine in patients with residual angina after PCI, we aimed to quantify the clinical benefits of adding ivabradine to standard antischemic therapy, in symptomatic patients for residual myocardial ischemia after PCI, using more precise indicators of oxygen consumption.

Furthermore, we studied the effects of ivabradine on diastolic function (both at rest and after exercise) and on the ventricular remodeling.

METHODS.

We investigated the efficacy of treatments with Ivabradine in addition to full anti-ischemic therapy (as per guidelines) compared with the latter alone in patients with signs or symptoms of residual angina underwent percutaneous coronary intervention plus stent implantation. The main purpose was to evaluate if addition of ivabradine to standard therapy might increase the threshold for angina improving the stress tolerance and exercise duration in terms of double product (DP) and triple product (TP), respectively calculated as a product between HR and systolic blood pressure and the product between DP and ejection time. In our opinion these, indirectly, reflect the true myocardial oxygen consumption (MVO₂) and the improvement of mechanical load that the ventricle can withstand at different levels of exercise. Triple product is closely related to the tension-time index, a measure of ventricular work and oxygen demand that is found by multiplying the average pressure in the ventricle during the period in which it ejects blood by the time it takes to do this [10].

The second objective was to evaluate changes at rest and after the stress test of diastolic function and ventricular remodeling, using echocardiographic parameters.

Study Population

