In this randomized, prospective, single-center study, all the patients selected were with chronic coronary artery disease undergoing percutaneous coronary intervention (PCI) plus stent implantation, residual angina and on treatment with full anti-ischemic therapy with and without Ivabradine. In all patients, revascularization was complete as far as possible, all coronary lesions resulting in a stenosis greater than 50% in vessels of a caliber greater than two millimeters were treated. The inclusion criteria was: coronary artery disease with chronic stable angina for more than three months (Canadian Cardiovascular Society–CCS-class I-III); percutaneous revascularization with stent implantation at least one; signs/symptoms of residual ischemia; sinus rhythm; HR \geq 70 bpm at rest; ability to perform an echocardiogram stress test with the tilting bicycle stress test (BST); good acoustic window; age \geq 18 years. The main exclusion criteria were: drugs intolerance or hypersensitivity, EF \leq 40 % with NYHA class III to IV; CCS IV; atrial fibrillation or flutter; presence of a pacemaker or implantable defibrillator; II or III degree AV block; HR \leq 70 bpm at rest or sick sinus syndrome; any condition that could interfere with the ability to exercise stress test like Wolff- Parkinson-White syndrome, left bundle branch block, left ventricular hypertrophy; rate-corrected QT interval (QTc) greater than 500 ms or the use of drugs that prolong the QTc interval; symptomatic hypotension or uncontrolled hypertension (systolic blood pressure at rest \geq 180 mmHg or diastolic blood pressure \geq 100 mmHg); severe liver disease and severe renal impairment (creatinine clearance \leq 30 ml/min); electrolyte disorders; uncontrolled thyroid disease and pregnancy. All patients signed informed consent prior to randomization. The study was designed according to the principles outlined in the Declaration of Helsinki and was approved by the Ethics Committee and Institutional Review.

Study design and Treatment

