Stress test was interrupted if the patient developed chest pain, ST segment elevation > 0.1 mV at 80 ms from the J point, or a significant adverse event (significant ventricular arrhythmia, limiting breathlessness, dizziness, muscular exhaustion, chest pain, arterial pressure drop ≥ 10 mmHg with symptoms, or severe systemic hypertension).

Echocardiography. Images were acquired in standard views and displayed side by side in a quad-screen format. All images were digitally recorded in continuous-loop format. Total work at the ischemic threshold and peak exercise were calculated. Double product (DP) was calculated during the last stage of exercise performed by multiplying maximum systolic BP by maximum HR; triple product (TP), was obtained integrating DP with ejection time (ET) measured with mitral annular PW-TDI (BP x SBP x ET).

In addition diastolic function was evaluated by PW Doppler E and A waves, TDI derived E' measurements and E/E' ratio. Mitral annular E' velocity was estimated as the average between lateral and septal velocity.

Drugs with possible interactions with ivabradine such as non-dihydropyridine calcium channel blockers, class I antiarrhythmics and strong inhibitors of cytochrome P450 3A4, were not allowed, whereas short-acting nitrates were allowed up to 3 hours before exercise or after exercise if needed. At the end of the tests, double, triple products and diastolic function evaluation, were collected by a blind operator.

All parameters recorded and calculated in off-line analysis were included in our register.

Statistical analysis.

The sample size was not calculated because it was a pilot study. Continuous variables were presented as mean \pm standard deviation (SD) and categorical variables as percentages. Categorical variables were compared among groups using the chi-square test or Fisher's exact test when appropriate, whereas continuous variables were compared with Student t-test. All tests were two-sided and a *p* value less than 0.05 was considered statistically significant. All analyses were performed using SPSS software, version 20.0 for Windows.

COMPLIANCE WITH ETHICAL STANDARDS

All authors declare that they have no conflict of interests. No funding was received for this study.

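### The only stated masking can leak: the blind operator collects heart-rate-based products together with the image readings, and heart rate is a partial clue to the arm

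*Combined protocol and SAP*

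**What the plan says.** The masking statement is one sentence in the Echocardiography paragraph: "At the end of the tests, double, triple products and diastolic function evaluation, were collected by a blind operator". The plan does not define what this operator is blind to.

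The same paragraph defines DP: "Double product (DP) was calculated during the last stage of exercise performed by multiplying maximum systolic BP by maximum HR". TP "was obtained integrating DP with ejection time (ET) measured with mitral annular PW-TDI (BP x SBP x ET"). The first factor printed there is BP, but Methods gives the products as "respectively calculated as a product between HR and systolic blood pressure and the product between DP and ejection time", so HR enters both. Methods also makes these two products the main efficacy measures. Diastolic function (E, A, E' and E/E') belongs to the second objective.

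The Introduction describes the drug as "resulting in selective HR reduction with no negative effects on blood pressure and inotropism". Study Population requires a resting HR of roughly 70 bpm or more. Study design and Treatment compares ivabradine with guideline standard therapy at 1:1, describes no placebo, and says that both strategies are titrated to the maximum tolerated dose, beta-blockers in particular. Stress echocardiography is done at T1 and at T2, 30 days later, with recordings before and during exercise.

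On storage, the plan says: "All images were digitally recorded in continuous-loop format". Off-line analysis is mentioned without any masking rule.

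**The concern.** Without a described placebo, the blind operator is the only stated protection against assessment bias. As written, that person assembles HR-based outcomes and also produces the image readings. The drug's declared effect is on HR, so a low T2 value, or a clear fall from T1, says something about the arm. The plan does not mention masking HR or visit, randomising the reading order, or giving HR and blood pressure to someone else.

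A reader who suspects the arm could tilt ejection time, and with it TP, or the velocities E, A and E'. TP belongs to the main purpose and the diastolic indices to the second objective. Pilot status does not remove the issue, because the plan still tests at two-sided 0.05.

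**Working it through.** **1. Which outcomes a reader can move**

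| Outcome | Inputs under the plan | Image reading involved? |
|---|---|---|
| DP | maximum systolic BP, maximum HR | No |
| TP | DP and ejection time from tissue Doppler | Yes, ejection time |
| E, A, E', E/E' | Doppler and tissue Doppler | Yes |

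TP is proportional to ejection time, so a given percentage shift in ejection time passes to TP in full. DP cannot be moved this way.

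**2. Inputs.** From the documents: 1:1 allocation and two-sided alpha 0.05. The plan gives no HR effect, no SD and no sample size, so there is no figure of its own to reproduce. Everything else below is assumed.

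**3. How well HR reveals the arm.** For normal HR with equal SD in two equal arms, the best guess is right with probability Phi(difference / (2 x SD)).

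| Assumed HR difference (bpm) | Assumed SD (bpm) | Correct guesses |
|---|---|---|
| 0 | any | 50% |
| 5 | 15 to 10 | 57-60% |
| 8 | 10 | 66% |
| 10 | 10 | 69% |
| 10, on change from T1 | 7 | 76% |
| 15 | 8 | 83% |

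**4. From guess to false difference.** If the reader shifts readings by b between guessed arms, wrong guesses cancel part of the shift. The net false difference is b x (2 x accuracy - 1).

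- Smallest case: b = 2%, accuracy 0.655. Net = 2 x 0.31 = 0.62% of mean TP.
- Largest case: b = 4%, accuracy 0.826. Net = 4 x 0.652 = 2.61% of mean TP.

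**5. From false difference to error rate.** Assume 20 per arm and a TP SD of 20-25% of the mean. The standard error is SD x sqrt(2/20): 20 x 0.316 = 6.32% or 25 x 0.316 = 7.91%. With k = net / standard error, the type I error is P(|Z + k| > 1.96).

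- Smallest case: k = 0.62 / 7.91 = 0.078, error 5.1%.
- Largest case: k = 2.61 / 6.32 = 0.412, error 7.0%.

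**6. Sensitivity.** If 2-4% is the net between-arm shift, which with b = 2-4% would need every guess to be right, k runs from 2 / 7.91 = 0.253 to 4 / 6.32 = 0.632 and the error from 5.7% to 9.7%. At 70% accuracy the factor is 2 x 0.70 - 1 = 0.40, so a net 2-4% needs a reader shift of 2 / 0.40 = 5% to 4 / 0.40 = 10% between guessed arms.

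**The case against.** The strongest reply is that HR is a weak clue here. Control patients are also titrated to the maximum tolerated dose, with beta-blockers singled out, so their HR may fall too. DP and TP use HR at the last exercise stage, whereas the entry threshold concerns resting HR. If ivabradine patients exercise longer, peak HR need not separate the arms by 8-15 bpm. At a 5 bpm difference with SD 10-15, guessing is only slightly better than chance.

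This stands as a limit on size. It does not close the route: diastolic function is assessed at rest as well as after stress, and nothing in the plan keeps resting HR or visit from the reader.

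A second reply is that the protocol is short and its silence proves nothing. Someone else may have supplied HR, and the documents do not say how far the Doppler readings depend on operator judgement. That is fair. The text shows an unprotected path, not that HR was seen or that any reading was biased.

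A reader might infer that the procedure undoes the blind for every variable the sentence names. The documents do not support that: a probabilistic clue weakens masking without voiding it, and DP contains no image reading to tilt.

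**Conclusion.** The point holds as a leak in the only stated masking. It concerns ejection time (hence TP) and E, A and E'. On the assumptions in the working (66-83% correct guesses, a 2-4% shift between guessed arms, TP SD 20-25% of the mean, 20 per arm), the nominal 5% error becomes about 5.1-7.0%. All four inputs are assumptions, and the documents cannot confirm any of them.

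A reader might infer inflation to 6-10%. That range follows only if the 2-4% is already the net difference between arms, or if the reader's shift is correspondingly larger. Nothing in the documents supports either.

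This is a modest weakness that merits a cheap improvement; it does not by itself invalidate the comparison.

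**What to change.** Rewrite the masking sentence in the Echocardiography paragraph so that:

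- the blind operator reads only ejection time, E, A and E' from the stored loops;
- T1 and T2 loops of all patients are pooled and read in random order, with patient, date, visit and the HR display masked;
- maximum HR and systolic BP are taken from the exercise record;
- DP and TP are computed by formula after the image readings are locked.

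Masking the visit matters most, because it hides the change in HR from T1, which is likely to be the strongest clue.

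The cost is protocol wording and file preparation, using the same operator and the loops already stored. Reading must wait for T2 and be done in batches, and beat spacing within a loop still gives a partial clue to rate. The change also does not reach the operators who run the exercise test. They are not described as blind, and peak HR and systolic BP depend on when the test ends.

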All patients with CCS I-III angina, were considered and only patients who met the inclusion criteria, after signing the informed consent form, were included in our study. The treatment was assigned on the basis of a 1:1 ratio to receive Ivabradine 5 mg twice daily (Ivabradine Group, IG) or standard therapy according to the guidelines (Control Group, CG). Both therapeutic strategies were titrated to the maximum tolerated dose, in particular β -blockers. All patients were submitted to clinical evaluation and exercise stress echocardiography at enrollment time (T1) and after 30 days of therapy (T2). During the period between exercise stress tests, clinical evaluation with ivabradine therapy up-titration was performed after 15 days.

Patient evaluation included physical examination, HR measurement by 12-lead electrocardiograms (ECG), two-dimensional, Doppler and Tissue Doppler echocardiography, using Philips iE33 system (Andover, Massachusetts, USA) and a supine bicycle ergometer stress test. During the test, operators recorded echocardiograms before and during the exercise. The parameters measured were: left ventricular (LV) 2D diameters, systolic function parameters, ejection time, LV end-systolic and end-diastolic volumes in relation to body surface area (end-diastolic and end-systolic indices [EDI and ESI]), and LV ejection fraction (LVEF) were assessed according to Simpson's method (as suggested by the American Society of Echocardiography and European Association of Echocardiography) [11].

Bicycle Stress Test. Exercise test, was performed using a semi-recumbent and tilting bicycle ergometer (X-SCRIBE EKG Analysis, Mortara Instruments; Ergometrics 800s, Ergoline West-Germany) with an initial workload set at 25 Watt and increments of 25Watt/ 2 min. HR and rhythm is continuously recorded using a 12-lead electrocardiogram, blood pressure was measured at baseline, at peak exercise, and during the last minute of each stage including recovery.

The rate of exercise, which was measured in metabolic equivalents (1 metabolic equivalent = 3.6 ml/kg/min), and the duration of exercise were assessed as well.

Chronotropic reserve was estimated using the formula: $100 \times (\text{peak HR} - \text{resting HR}) / (220 - \text{age}) - \text{resting HR}$.

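### Blind reading is stated only for double product, triple product and diastolic function, so the plan lets LV diameters, volumes and LVEF be traced with the arm known

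*Combined protocol and SAP*

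**What the plan says.** Under Study design and Treatment, patients are assigned 1:1 to "receive Ivabradine 5 mg twice daily (Ivabradine Group, IG) or standard therapy according to the guidelines (Control Group, CG"). No placebo or other masking of treatment is described. Between the two stress tests, "clinical evaluation with ivabradine therapy up-titration was performed after 15 days".

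The same section lists the echocardiographic measures: LV diameters, systolic function parameters, ejection time, "LV end-systolic and end-diastolic volumes in relation to body surface area" (EDI and ESI), and LVEF by Simpson's method. On acquisition it says: "During the test, operators recorded echocardiograms before and during the exercise". It does not say whether those operators know the arm.

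The Echocardiography paragraph states that "All images were digitally recorded in continuous-loop format" and contains the only sentence on blinding: "double, triple products and diastolic function evaluation, were collected by a blind operator". A later sentence mentions off-line analysis without naming the reader or saying that the reader is blind.

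The Methods section makes ventricular remodelling, together with diastolic function, the second objective. It places the angina threshold, stress tolerance and exercise duration in the main purpose, expressed through double product (DP) and triple product (TP).

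DP is taken at the last stage of exercise performed, and TP is built from DP. The events that end the test include "limiting breathlessness, dizziness, muscular exhaustion, chest pain".

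**The concern.** The second objective has two parts, and the plan blinds one of them. Diastolic function goes to a blind operator. The remodelling measures have no stated blinding, and no reason is given for the difference. Because three items are named, a reader cannot assume that the rest are covered.

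Volumes and LVEF by Simpson's method depend on an operator tracing the endocardial border. A reader who knows the arm and the visit can, without intending to, trace in the direction expected of the new drug. A shift of that kind does not average out over patients. It enters the between-arm difference directly and raises the chance of declaring a remodelling effect where none exists.

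A second and separate issue sits behind the words on blind collection. DP and TP are fixed by the stage at which exercise ends. If patient and staff know the arm, a blind operator collects a value that an unmasked decision may already have shaped.

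**Working it through.** **Step 1: which measures have stated blinding**

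| Measure | Objective served | Blinding stated? | Can stored loops be read blind? |
|---|---|---|---|
| DP, TP | Main purpose | Collection: yes. Stop decision: not stated | Does not change the stop |
| Diastolic indices | Second objective | Yes | Already covered |
| LV diameters, EDI, ESI, LVEF | Second objective (remodelling) | No | Yes |
| Exercise duration, work at ischaemic threshold | Main purpose | No | No: test is ended live, threshold undefined |

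The third row is a gap that the stored loops can close. The first and fourth rows have a limit that they cannot remove.

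**Step 2: is knowledge of the arm likely?** The comparator is standard therapy, no placebo or masking is described, and the day-15 visit is tied to up-titration of ivabradine. The protocol does not use the term open-label. It is an inference from these three facts.

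**Step 3: size, as an illustration.** The plan has no figure to reproduce: the Statistical analysis section says that sample size was not calculated, and no SD is given.

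Inputs from the plan: Student t-test, two-sided, 5% level. Assumed inputs: n = 20, 30 or 50 per arm; no true drug effect; a systematic reader difference between arms of b = 0.1, 0.2 or 0.3 SD.

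With df = 2n − 2, the test statistic follows a non-central t distribution with non-centrality δ = b × √(n/2). The false-positive rate is P(T > c) + P(T < −c), where c is the 97.5% point of central t.

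| n per arm | c | δ at b = 0.1 | Rate | δ at b = 0.2 | Rate | δ at b = 0.3 | Rate |
|---|---|---|---|---|---|---|---|
| 20 | 2.024 | 0.316 | 0.061 | 0.632 | 0.095 | 0.949 | 0.152 |
| 30 | 2.002 | 0.387 | 0.067 | 0.775 | 0.119 | 1.162 | 0.208 |
| 50 | 1.984 | 0.500 | 0.079 | 1.000 | 0.168 | 1.500 | 0.318 |

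With b = 0 the rate is 0.050 in every row. A normal approximation gives nearly the same values (at b = 0.3: 0.158, 0.213 and 0.323). For a fixed shift the rate rises with n, so a larger trial does not dilute this bias.

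The table applies to a shift in reading. It does not measure the effect of stopping a test early or late, which blind reading would leave unchanged.

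**The case against.** The strongest reply is that the protocol does not say that volumes or LVEF were read unblinded. It is silent, and the same blind operator may have read them off-line. That stands as far as it goes: the defect is that the plan permits unblinded tracing, and the text does not show that it happened. Silence is still not a safeguard when the only blinding sentence gives a list.

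A second reply is that the benefit is limited. The main purpose is expressed through DP and TP, whose collection is already blind. Remodelling is a second objective of a pilot study. Ivabradine lowers heart rate, so the rate on a T2 loop may reveal the arm. All of this is fair, and it keeps the point modest. Partial masking with visit and order concealed is still better than none.

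A third reply is that the size is assumption throughout. That is correct. At 0.1 SD the inflation is small (6-8%).

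A reader might infer more than the documents support in three ways:

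- **That the stored loops would also blind the ischaemic-threshold measures.** They would not. The protocol never defines the threshold or ties it to wall motion, and several of the events that end the test are symptoms, which no loop records.
- **That blind reading would repair DP, TP and duration.** It cannot change when the test was stopped.
- **That the change needs no extra resource.** The documents do not describe reader numbers or workload.

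**Conclusion.** The point holds for LV diameters, EDI, ESI and LVEF. They serve a stated objective, they are traced by an operator, they have no stated blinding, and no treatment masking is described. The plan therefore allows them to be read with the arm known, although the means to avoid this (stored loops, off-line analysis and a blind operator) are already in it.

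Under an assumed shift of 0.1 to 0.3 SD, the nominal 5% false-positive rate becomes 6-15%, 7-21% or 8-32% at 20, 30 or 50 per arm. These figures illustrate the mechanism. They do not estimate the bias in this trial, since neither the shift nor N comes from the protocol.

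For DP, TP, exercise duration and work at the ischaemic threshold, the conclusion is narrower. Blind collection does not protect them from a live stop decision by patients and staff who may know the arm, and that limit has to be reported. The change is worth making. It does not call for a redesign.

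**What to change.** Amend the blinding sentence in the Echocardiography paragraph along these lines: *LV diameters, EDI, ESI and LVEF, as well as DP, TP and the diastolic indices, are measured off-line from the stored recordings by the blind operator, with arm and visit (T1 or T2) masked and studies read in random order.*

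Separately, for the outcomes that depend on when exercise ends:

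- State who determines the ischaemic threshold and who ends the test, and whether they know the arm.
- Record the reason for stopping in every test and tabulate it by arm.
- Say in the conclusion that last-stage DP and TP, exercise duration and work at the threshold came from an effort-dependent test whose end was not shown to be masked.

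Cost: one amended sentence, one recorded item per test and one table. The blind operator needs more time for reading, masking and random ordering, and the documents give no basis for saying how much. Masking will remain partial because heart rate is visible on the loops, and the report should say so.

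### Continuous outcomes are measured at T1 and T2 but compared by a plain t-test, so the baseline value is ignored or used inefficiently

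*Combined protocol and SAP*

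**What the plan says.** Under Study design and Treatment, every patient has clinical evaluation and "exercise stress echocardiography at enrollment time (T1) and after 30 days of therapy (T2". Double product, triple product, exercise duration, LV volumes and the diastolic indices are therefore planned at both times.

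The objectives in Methods are framed as improvement or change. The main one asks whether ivabradine raises the angina threshold, "improving the stress tolerance and exercise duration in terms of double product (DP) and triple product (TP". For the other: "The second objective was to evaluate changes at rest and after the stress test of diastolic function and ventricular remodeling".

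The Statistical analysis section covers all continuous outcomes in one clause: "whereas continuous variables were compared with Student t-test". It names no covariate, ANCOVA or repeated-measures model. It does not say whether the test is applied to T2 values, to T2 minus T1, or within an arm. It adds: "All tests were two-sided and a *p* value less than 0.05 was considered statistically significant".

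On size: "The sample size was not calculated because it was a pilot study". On allocation: "The treatment was assigned on the basis of a 1:1 ratio". No stratification is described.

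**The concern.** A baseline value of the same outcome is usually the best available predictor of its follow-up value. The clause on the t-test can be read in three ways:

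- **T2 compared between arms.** The T1 data are discarded.
- **Change compared between arms.** T1 is used, but with a fixed weight of 1 instead of the weight the data support.
- **T1 against T2 within an arm.** This is not a randomised comparison. It mixes any drug effect with learning, regression to the mean and concurrent titration of background therapy.

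Two things are at stake. One is precision, in a study with no planned size to absorb the loss. The other is how far a chance difference between arms at T1 carries into the estimate when nothing adjusts for it. Leaving the tested quantity open also lets the choice be made after the data are seen.

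**Working it through.** The plan gives no sample size, SD, effect size or power, so there is no stated figure to reproduce. The check compares the candidate analyses.

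**Inputs from the documents:** measurements at T1 and T2; 1:1 randomisation; t-test for continuous variables; two-sided 0.05.

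**Assumptions, not in the documents:** T1–T2 correlation *r* from 0.3 to 0.8; 15 to 30 patients per arm; the same SD at T1 and T2 and in both arms.

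**Step 1: variance of the between-arm difference,** relative to a t-test on T2 (= 1)

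- t-test on change: 2(1 − *r*)
- ANCOVA on T1: 1 − *r*²
- ANCOVA relative to change: (1 − *r*²) / [2(1 − *r*)] = (1 + *r*)/2

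The reduction in CI width is 1 − √(variance ratio). The equivalent extra patients are 1/(variance ratio) − 1.

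| *r* | ANCOVA ÷ T2-only | CI narrower by | Worth extra patients | ANCOVA ÷ change | CI narrower by | Worth extra patients |
|---|---|---|---|---|---|---|
| 0.3 | 0.91 | 5% | 10% | 0.65 | 19% | 54% |
| 0.5 | 0.75 | 13% | 33% | 0.75 | 13% | 33% |
| 0.6 | 0.64 | 20% | 56% | 0.80 | 11% | 25% |
| 0.7 | 0.51 | 29% | 96% | 0.85 | 8% | 18% |
| 0.8 | 0.36 | 40% | 178% | 0.90 | 5% | 11% |

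Example at *r* = 0.6: 1 − 0.36 = 0.64; √0.64 = 0.80, so the CI is 20% narrower; 1/0.64 = 1.56, so 56% more patients would be needed to match it.

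**Step 2: cost of estimating the slope.** The variance rises by roughly 1/(N − 4), with N the total. At 20 per arm this is 1/36, or about 3%. ANCOVA then beats the T2-only test when (1 − *r*²)(37/36) < 1, that is *r* above about 0.16. It beats change scores when [(1 + *r*)/2](37/36) < 1, that is *r* below about 0.95.

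**Step 3: chance imbalance.** With *n* per arm, the baseline difference has SD √(2/*n*) in baseline SD units, so its 95% limit is 1.96√(2/*n*). Given an imbalance *b*, the T2-only estimate shifts by *r* × *b* and the change-score estimate by (*r* − 1) × *b*. ANCOVA removes the shift under a linear model.

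| *n* per arm | 95% limit of imbalance | T2-only shift at *r* = 0.6 |
|---|---|---|
| 15 | 0.72 SD | 0.43 SD |
| 20 | 0.62 SD | 0.37 SD |
| 30 | 0.51 SD | 0.30 SD |

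At 20 per arm the change-score shift at the same limit is (0.6 − 1) × 0.62 = −0.25 SD. A smaller imbalance is common: the chance that it exceeds 0.25 SD is 43% at 20 per arm, which would shift the T2-only estimate by 0.6 × 0.25 = 0.15 SD.

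**The case against.** The strongest reply is that the planned test is not wrong. Under 1:1 randomisation an unadjusted between-arm t-test is unbiased on average and keeps its 5% type I error, because its standard error already includes chance baseline variation. This stands. The shift in Step 3 is the precision loss of Step 1 seen from another side, not a second harm, and 0.37 SD is an outer limit, not a typical value.

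Second, the size depends on an undefined comparator. The secondary objective speaks of changes; if change scores are what is tested, the gain at correlations of 0.5 to 0.7 is 8–13% in CI width, not 13–29%, and only 5% at 0.8. This also stands, which is why both comparators are shown. It does not rescue the plan, since ANCOVA is better than either over the whole range tabulated.

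Third, the correlation and the arm sizes are assumptions, and a small sample is inferred from the word pilot. True; the direction of the result does not depend on them, but its size does.

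Fourth, the grammar of the clause suggests comparison between groups, and no within-arm test is actually planned. That is the more natural reading, so the within-arm point is only a guard against ambiguity.

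Fifth, one listed measure, total work at the ischaemic threshold, exists only if a threshold is reached, so its T1 value may be missing in some patients. This calls for a rule for that outcome and leaves the rest unaffected.

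**Conclusion.** The concern holds. The plan collects a baseline for its continuous outcomes and specifies no analysis that uses it well. For assumed correlations of 0.5 to 0.7, the avoidable loss is 13–29% in CI width if T2 values are tested and 13–8% if changes are tested. Over 0.3 to 0.8 it runs from 5% to 40% and from 19% to 5% respectively. At an assumed 15 to 30 per arm and correlation 0.6, an imbalance at its 95% limit would displace an unadjusted T2 estimate by 0.43 to 0.30 SD. This is a matter of efficiency and of conditional error given the observed imbalance, not an invalid test. It should be changed because the remedy is almost free and the study has no calculated sample size to offset the loss.

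**What to change.** Replace the t-test clause for outcomes with a rule on these lines: for each continuous outcome, the arms are compared at T2 by ANCOVA, with treatment as factor and the T1 value of that outcome, taken in the same state (rest or exercise), as covariate; the adjusted mean difference is reported with its 95% CI. State that within-arm T1–T2 comparisons are descriptive only, and how patients without a T1 value are handled where an outcome may be undefined.

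The cost is a sentence or two in the statistical section and one degree of freedom per model, with no new data.

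The section is written in the past tense, and a document dated 2015 lists a 2018 reference. If outcome data had already been examined, the ANCOVA should be labelled as added afterwards and reported beside the t-test.
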